#### Adherence

- We will determine what proportion of participants in the home BP arm successfully complete home BP training, perform home BP readings every other week and transmit data in a timely manner to the study team via any method.
- We will determine the drop out and completion rate in each arm.

#### Safety

- We will monitor for excessively low blood pressure readings (e.g. dialysis unit blood pressure readings of <90 mmHg) and dangerous consequences of excessively low blood pressure (e.g. syncope, falls).
- We will monitor for excessively high blood pressure readings (e.g. dialysis unit blood pressure readings of >200 mmHg) and dangerous consequences of excessively high blood pressure (e.g. flash pulmonary edema).

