### 8.2.3 Blood pressure: Assessment of episodes and symptoms of intra-dialytic hypotension

We will review the dialysis record approximately every 2 weeks for all study participants to determine frequency of intra-dialytic hypotension (IDH; defined as intra-dialytic SBP<90 mmHg). This will be obtained from the dialysis unit medical record and quantified as % of sessions with IDH over the 4-month study duration. For symptoms assessment, we will contact participants (in both arms) once approximately every 2 weeks. Patients will be queried via interview (either phone or during dialysis) about adverse events noted during the past HD session(s) which will include symptoms of hypotension such as cramping (yes/no), dizziness/lightheadedness (yes/no) and fatigue (yes/no). We will also ask patients “how long did it take you to recover from your last dialysis treatment,” a validated question that is an important patient-centered outcome. Patient responses to this question will be reported in minutes.

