## **9.3 Visits 2-8 (occurring approximately every 2 weeks)**

1. Record any Adverse Experiences
2. Review any home BP measures (if applicable)
3. Concomitant medications review
4. Updated medical history/interim events/interim hospitalizations
5. BP medication review and assessment of adherence to BP medications

6. Review dialysis unit records: estimated dry weight, pre-dialysis blood pressures, episodes of intra-dialytic hypotension
7. Record any updated laboratory values (with corresponding date) taken from the dialysis records
8. Record vital signs, including weight and dialysis unit BP
9. Administer questionnaire of symptoms of hypotension during the last hemodialysis session: cramping (yes/no), dizziness/lightheadedness (yes/no), and fatigue (yes/no).
10. Ask open-ended question: "How long did it take you to recover from your last dialysis session" (responses in minutes or hours)
11. If subject is a woman of child-bearing age, she will also be asked about possible pregnancy (UW only).
12. Adjust estimated dry weight and medications as per study physician's recommendations

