## **10 ADVERSE EXPERIENCE REPORTING AND DOCUMENTATION**

### **10.1 Adverse Events**

An adverse event (AE) is any untoward medical occurrence during a clinical investigation and that does not necessarily have a causal relationship with the study intervention. An AE is therefore any unfavorable and unintended sign (including an abnormal laboratory finding), symptom or disease that may or may not be associated with the administration of a study intervention.

The study team will probe, via discussion with the subject and review of the medical record, for the occurrence of AEs during each subject visit and record the information in the site's source documents. Adverse events will be recorded in the patient CRF. Adverse events will be described by duration (start and stop dates and times), severity, outcome, treatment and relation to study intervention, or if unrelated, the cause.

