### **10.2.1 Serious Adverse Experience Reporting**

Study sites will document all SAEs that occur (whether or not related to study drug) per UCSF CHR and UW IRB Guidelines. The collection period for all SAEs will begin after informed consent is obtained and end after procedures for the final study visit have been completed.

In accordance with the standard operating procedures and policies of the local Institutional Review Board (IRB), the site investigator will report SAEs to the IRB.

We will collect data on potential adverse events from several sources and incorporate them into the adverse event database. These sources include:

- Reports from participants of any occurrences of concern to them, to be obtained from calls to toll-free or local study numbers provided in the Consent Form and included in all post-enrollment Contact Forms
- Laboratory database and reports of new hospitalizations

Adverse events data from the study-site specific call lines will be reviewed weekly, as will AE reports from all sources, by the site PI and site study clinician(s), any Serious Adverse Events that are identified will be reported promptly to the DSMB and IRB(s).

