## APPENDIX 1.

	VISIT 0 SCREENING VISIT	VISIT 1 Baseline Visit	VISITS 2-8 (in person during regularly scheduled dialysis or phone call) 14 (+/-7) days apart	VISIT 9
Informed Consent	X			
Medical History	X	X	X	X
Recording of vital signs, including blood pressure and weight	X	X	X	X
Review of medical and dialysis records	X	X	X	X
Medication review	X	X	X	X
Record laboratory values	X	X	X	X
Questionnaires on episodes and symptoms of high or low blood pressure	X	X	X	X
Randomization		X		
Teaching of home BP monitor		X		
Reviewing BP medications and pre- and post-dialysis weights			X	X
Review home BP readings (if applicable)			X	X
Concomitant Medication Review			X	X
Adjust EDW or BP medications			X	X
Adverse Experiences			X	X
44-hour ambulatory blood pressure monitor		X		X
Blood draw		X		X

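### Syncope, falls and flash pulmonary edema belong to the primary safety outcome but have no structured question or definition, so untreated events at home are likely to be undercounted

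*Combined protocol and SAP*

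**What the plan says.** Section 5.1 lists four primary outcomes, one of which is Safety. Under it the study will monitor very low and very high dialysis-unit readings and also their clinical results: "dangerous consequences of excessively low blood pressure (e.g. syncope, falls") and "dangerous consequences of excessively high blood pressure (e.g. flash pulmonary edema"). All three events are given as examples, without case definitions.

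The participant questionnaire is itemised in the visit schedule. Section 9.3 (Visits 2-8) reads "Administer questionnaire of symptoms of hypotension during the last hemodialysis session: cramping (yes/no), dizziness/lightheadedness (yes/no), and fatigue (yes/no"), followed by a recovery-time question. Section 9.4 repeats these procedures at Visit 9. Section 9.1 has the same three symptoms at screening, for the last session or sessions. Section 8.2.3 describes the interview as covering "adverse events noted during the past HD session(s) which will include symptoms of hypotension such as cramping (yes/no), dizziness/lightheadedness (yes/no) and fatigue (yes/no").

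Appendix 1 gives the instrument a wider scope: "Questionnaires on episodes and symptoms of high or low blood pressure".

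Separate channels exist for adverse events. Section 10.1 has the team probe "via discussion with the subject and review of the medical record, for the occurrence of AEs during each subject visit". Section 9.3 includes "Updated medical history/interim events/interim hospitalizations". Section 10.2.1 adds laboratory data, reports of new hospitalizations, and "Reports from participants of any occurrences of concern to them". Section 14.3 tabulates adverse events by treatment group, with number of patients, rate, severity and relationship. Section 7.2 states that neither investigators nor participants are blinded.

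**The concern.** The protocol names specific clinical events as part of a primary outcome, then describes a two-weekly structured interview that asks about other things. The interview concerns how the participant felt around a dialysis session. A faint or a fall can happen at any time, and for a blood pressure strategy the hours away from the unit matter as much as the hours in it.

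For an event that brings the participant to medical attention this matters little, because other channels should find it. For one that does not, such as a fall at home with no injury or a brief faint, the count depends on whether a general conversation happens to bring it out. Such counts tend to be low and to vary with the interviewer. With 25 participants per arm, one or two missed events would change the safety picture that the pilot hands to the design of a larger trial.

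**Working it through.** The plan states no event rate, detection rate or power figure for these outcomes, so there is nothing to reproduce. The check compares the outcome definition with each means of collecting it, with simple arithmetic on the recall period.

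**Inputs**
- Dialysis frequency: three sessions per week (6.2).
- Interval between contacts: 14 days, plus or minus 7 (Appendix 1).
- Follow-up contacts: Visits 2 to 9, which is 8 contacts (9.3, 9.4).
- Follow-up length: 4 months (4.1), taken here as 16 weeks, which is 8 intervals of 14 days.
- Recall period in 9.3: the last session.

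**Share of sessions covered by the 9.3 recall period**

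Sessions per interval = 3 × days / 7. Share covered = 1 / sessions.
- 7 days: 3 × 7/7 = 3 sessions; 1/3 = 33%.
- 14 days: 3 × 14/7 = 6 sessions; 1/6 = 17%.
- 21 days: 3 × 21/7 = 9 sessions; 1/9 = 11%.
- Whole study: 3 × 16 = 48 sessions; 8/48 = 17%.

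These shares apply to the three listed symptoms. For syncope, falls and pulmonary edema the itemised list contains no question at all. Adding items under the same recall period would still leave out five of six sessions and all the time between sessions, so the period has to change along with the items.

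**What each source would find**
- Itemised questionnaire (9.1, 9.3, 9.4): none of the three events by name.
- Dialysis record review as itemised in 9.3 (dry weight, pre-dialysis pressures, intra-dialytic hypotension): not events at home.
- Medical record review, interim hospitalizations and hospitalization reports (10.1, 9.3, 10.2.1): events that led to care. Flash pulmonary edema would probably be among them, as would an injurious fall.
- Discussion of adverse events and interim events at each contact (10.1, 9.3): any event that the participant recalls and mentions, with no standard wording.
- Participant calls (10.2.1): events that the participant chooses to report.

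An untreated fall or faint at home is therefore open only to the last two sources.

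**Internal consistency**

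Appendix 1 says the questionnaires cover episodes as well as symptoms, and high as well as low pressure. The list in 9.3 has three symptoms of low pressure, no episodes and nothing on high pressure. The recall period also varies: a single session in 9.3 and under Tolerability in 5.1, but one or more sessions in 8.2.3 and 9.1.

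**Analysis**

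The adverse event table in 14.3 would include these events if they are recorded, but neither 14.3 nor the synopsis names them.

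**The case against.** The strongest reply is that the three-symptom interview is the tolerability measure, placed in 8.2.3 under intra-dialytic hypotension, and that safety is served by adverse event collection. That is a fair reading of the structure. It means the omission of falls from this interview is not in itself a contradiction. The mismatch with Appendix 1 remains, as does the lack of any structured question for a primary outcome anywhere in the text.

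Three stronger readings are tempting, and the documents do not support them.

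- A reader might infer that these events are captured only by open-ended probing, or are never asked about. Sections 9.3, 10.1 and 10.2.1 provide for interim events, record review, hospitalization reports and call lines. What is missing is a named item, not all inquiry.
- A reader might infer that the home arm is the one at risk, because its pressure away from dialysis is being targeted. Both arms share one target and one algorithm (4.1, 8.1). Section 2 reports that 166 of 269 patients (62%) with dialysis-unit systolic pressure above 140 mmHg were below 140 mmHg outside the unit, and it argues that targeting the unit reading may overtreat. Untreated events at home are a concern in either arm.
- A reader might infer a demonstrated bias between arms. Contacts follow the same schedule and content apart from review of home readings, and no capture rates are given. Lack of blinding makes unequal reporting possible; nothing in the documents shows its direction or size.

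Two further points stand. Sections 5.1 and 8.2.3 present the symptoms as examples, and the forms themselves are not in the documents, so a form may hold more items than the text. Section 14.5 says the pilot was not designed to find significant differences between arms, which limits the consequences.

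**Conclusion.** The point holds in a limited form. Three events named in a primary safety outcome have no structured question, no definition and no named row in the analysis. The itemised interview at follow-up covers about 17% of sessions (11% to 33% across the contact window) and no time between sessions, and it is narrower than Appendix 1 says. Events that lead to care are probably captured. Untreated falls and faints at home, in either arm, are likely to be undercounted.

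The number missed cannot be calculated, because the documents give neither an event rate nor a detection rate. The conclusion assumes that the forms follow the protocol text and that a direct question finds more such events than general inquiry does. It is a modest point, worth acting on because safety is a primary outcome and one purpose of the pilot is to test study logistics.

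**What to change.** 1. Add yes/no items to the existing interview for a fall, syncope, and pulmonary edema. For the last, urgent care for breathlessness can serve as the form that a participant is able to report; it is a proxy that 5.1 does not name, and the text should say so.
2. Word the items identically in both arms. Use *since the last contact* at Visits 2-9 and *in the past 2 weeks* at screening and baseline, where no comparable earlier contact exists.
3. Give each event a short definition in 5.1 or on the case report form.
4. Report the events as named rows in the by-arm adverse event table that 14.3 already plans. Section 14 says the detailed SAP is still to be written, so the rows can be specified there.
5. Reconcile the questionnaire in 9.1 and 9.3 with its description in Appendix 1, and use one recall period for the symptom items across 5.1, 8.2.3, 9.1 and 9.3.

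The cost is two or three items, about one minute per contact. Event counts will be somewhat higher than under general inquiry alone, and the report should say that this reflects direct questioning. No treatment rule changes.

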#### Tolerability

- We will review the dialysis record every 2 weeks to determine frequency of intra-dialytic hypotension, defined as SBP<90 mmHg during dialysis
- For symptoms assessment, we will contact participants (in both treatment groups) once every 2 weeks. Patients will be queried via interview (either phone or during dialysis) about adverse events noted during the immediate past HD session which will include symptoms of hypotension such as cramping (yes/no), dizziness/lightheadedness (yes/no) and fatigue (yes/no). We will

also ask patients “how long did it take you to recover from your last dialysis treatment.”

## 5.2 Secondary Outcomes

- Acceptability of a Bluetooth-enabled home BP monitor: of the home BP participants, we will determine the modality they choose to transmit their home BP readings (e.g. via Bluetooth, manual log, phone, etc)
- Differences in blood pressures between treatment groups as assessed by: (1) pre-dialysis SBP and DBP; (2) post-dialysis SBP and DBP and (3) 44-hour intra-dialytic ambulatory blood pressure monitoring from beginning to the end of the study (optional)

## 6 SUBJECT SELECTION

### 6.1 Study Population

Subjects with ESRD on maintenance in center hemodialysis who meet the inclusion and exclusion criteria will be eligible for participation in this study.

### 6.2 Inclusion Criteria

In order to be eligible to participate in this study, an individual must meet all of the following criteria:

1. Provision of signed and dated informed consent form
2. Undergoing in-center, thrice weekly hemodialysis for treatment of end stage renal disease
3. Greater than 3 months since initiation of dialysis
4. Aged 18 years or above
5. Able to obtain a brachial blood pressure at dialysis and at home

### 6.3 Exclusion Criteria

1. Pregnancy, anticipated pregnancy, or breastfeeding as this will require increase to more than three times a week dialysis and/or preclude use of some classes of blood pressure medications
2. Incarceration or institutionalized living which may prohibit measurement of home blood pressure
3. Participation in another intervention study that may affect blood pressure
4. Patients in whom systolic blood pressure is not measurable (e.g. those with left ventricular assist devices)
5. Hypotension: average pre-dialysis systolic blood pressure <100 mmHg over last 2 weeks prior to screening while not taking any blood pressure medications
6. Life expectancy <4 months
7. Anticipated living donor kidney transplant within 4 months

## 6.4 Strategies for Recruitment and Retention

- Target study sample size: Our target sample size is 50 participants (25 participants at UCSF and 25 participants at UW).
- Source of participants: outpatient hemodialysis units affiliated with UCSF and UW or where UCSF and UW faculty practice.
- We will use the Electronic Medical Record (EMR) or directly query dialysis healthcare providers at UCSF and UW to identify eligible participants. We may confer with the primary nephrologist prior to approaching the patient if there are concerns about the suitability of the patient to participate in a research study.
- Incentives: Participants will be provided \$25-50 per month for participation in the study, depending on the visit number and the site.

## 7 STUDY TREATMENTS

### 7.1 Method of Assigning Subjects to Treatment Groups

Enrolled subjects, stratified by site, will be randomly assigned in a 1:1 allocation to one of 2 groups (25 patients at both sites): (1) home SBP<140 mmHg and (2) in-center pre-dialysis SBP<140 mmHg. Randomization will be in done via Redcap in random size blocks to minimize bias in randomization and to ensure balanced assignment at each site. Both groups will be followed in parallel.

Prior to conducting any study-related activities, written informed consent and the Health Insurance Portability and Accountability Act (HIPAA) authorization must be signed and dated by the subject or subject's legal representative. If appropriate, assent must also be obtained prior to conducting any study-related activities.

### 7.2 Blinding

Due to the nature of the intervention, the study will not be blinded to either the investigators nor the study participants.

### 7.3 Measuring Home SBP

We will use the Microlife WatchBP Home A BT device.

After appropriate training by study personnel, study participants will be asked to take their own BP at home every two weeks.

- Home BP will be taken on a non-dialysis day
- Participants will be instructed to obtain a BP measure in the morning on a non-dialysis day (3 consecutive BP measures obtained at one sitting)
- Participants will be instructed to obtain a BP measure in the evening on a non-dialysis day (3 consecutive BP measures obtained at one sitting)

Participants will have several options to share the home blood pressure readings with the study team.

- For participants with a smart phone, the BP readings can be automatically downloaded via Bluetooth to an app then to a secure cloud server.
- Participants can download the readings from the home blood pressure device via USB drive and shared with the study team.
- Participants can keep a paper log of home blood pressure readings to share with the study team.
- Participants can text, phone or email the results to the study team.

We will allow assistance from family members or other caregivers and work in other ways with study participants to minimize burden of data transmission.

#### **7.4 Measurement of In-Center Pre-Dialysis SBP**

Pre-dialysis BP will be taken by an automated BP device by dialysis unit staff using regular dialysis unit equipment.

We will educate the dialysis unit staff and participants to allow patients to relax (ideally a 5 minute rest) prior to BP being measured and that the BP cuff should be placed over bare arm or a thin garment.

The pre-dialysis BP will be reviewed by the study team every 2 weeks.

#### **7.5 Treatment Adherence**

Participants in both treatment arms will have regular contact with the study coordinator (scheduled approximately every 2 weeks), where they will be reminded/encouraged to take all prescribed anti-hypertensive medications and medication reconciliation will be performed. For participants in the home BP treatment arm, home BP readings will be reviewed and assessed for adherence.

#### **7.6 Temporary Discontinuation**

Temporary discontinuation will be allowed in the study protocol in the event of hospitalization, travel out of town or other unavoidable breaks. Participants will be re-evaluated at hospital discharge or return to regular maintenance dialysis unit and resume participation in the trial barring any clinical contraindications. This mimics how study intervention would be implemented in actual clinical practice.

#### **7.7 Lost to Follow-Up**

A participant will be considered lost to follow-up if he or she fails to engage in participants contacts (either by phone or in the dialysis unit) of greater than 1 month and is unable to be contacted by the study site staff.

The following actions must be taken if a participant fails to engage in contacts with the study team :

- The site will attempt to contact the participant and counsel the participant on the importance of maintaining the assigned contact schedule and ascertain if the participant wishes to and/or should continue in the study.
- Before a participant is deemed lost to follow-up, the investigator or designee will make every effort to regain contact with the participant. These contact attempts should be documented in the participant's study file.
- Should the participant continue to be unreachable, he or she will be considered to have withdrawn from the study with a primary reason of lost to follow-up.

## 8 STUDY PROCEDURES AND GUIDELINES:

### 8.1 Approach to blood pressure management

For participants in the usual care treatment group, blood pressure readings measured for clinical purposes at the dialysis unit will be tracked, recorded and in response we will modify the dry weight and anti-hypertensive medications per algorithm below (including the date in which any adjustments to dry weight and medication dose were implemented).

For participants in the home blood pressure treatment group, we will track and record the home blood pressure measures and modify the dry weight and anti-hypertensive medications per algorithm below.

The following approach will be used to achieve SBP <140 mmHg and >100 in both treatment groups, which will be implemented every 2 weeks.

- Dry weight adjustment (with counseling on dietary sodium and fluid intake if appropriate)
- Adjustment of standard anti-hypertensive medications (e.g. angiotensin converting enzyme [ACE] inhibitors/angiotensin receptor blockers [ARB][collectively referred to as RAAS inhibitors];  $\beta$ -blockers; calcium channel blockers). The protocol will be as follows

